3.3. Approach

This project represents a partnership between AirCareLabs and the University of Pennsylvania Sleep Disorders Center. AirCareLabs has developed an innovative technology platform that focuses on the 30-day readmission period to create a seamless interface for patient-provider interactions and monitoring of disease metrics. The Penn Sleep Center is an internationally recognized leader in the field of sleep medicine, with over 15 active sleep medicine clinicians and an in-patient sleep consult service that, in preliminary data, has shown that sleep apnea treatment for heart failure patients has the potential to reduce readmission rates. However, the major limitation of the existing in-patient sleep consult service is the low adherence rate (approximately 30%) post-discharge, a limitation that can be effectively addressed using the AirCareLabs solution; this is the core proposition of the current protocol.

The proposed project Phase 1 includes the following key components: 1) Structured interviews with users/care providers; 2) Creating educational content; 3) Developing problem resolution care pathways; 4) Integration of Oximeter data;. The proposed project Phase II includes the following key components: 1) Integration of PAP adherence data; 2) Revising educational content and care pathways; 3) Developing risk classification criteria; and 4) Conducting a large randomized clinical trial to demonstrate effectiveness. These elements are described in more detail below.

We propose to utilize the Fast Track mechanism because the compelling preliminary data suggest the potential for a significant improvement in patient outcomes; all the elements of the program are in place to allow for implementation; and the rapid evolution of the competitive landscape relies upon a first-to-market approach to gather crucial market share to improve commercialization prospects.

3.3.1. Phase 1 Plan

3.3.1.1 Task 1.1: Structured interviews

We will conduct one-on-one interviews with key stakeholders—patients and sleep medicine providers (physicians/nurse practitioners, sleep study technicians). These interviews will be used to maximize usability, resolve potential problems with the user interface, and identify key educational content materials.

The interviews will be conducted by a team consisting of one interviewer ([name] and/or [name]) and a note-taker; this will allow the interviewer to focus on guiding the discussion. Interview participants will be compensated for their time at a rate consistent with their usual hourly salary. The general interview framework is as follows: 1) Open discussion during which the user/provider will be asked to discuss their understanding of heart failure, sleep apnea, and challenges associated with sleep apnea treatment, as well as the current solutions they have attempted to use; 2) A demonstration of the AirCareLabs system, including patient survey feature, assistance request mechanism, and videochat features; 3) Semi-structured interview of their experience with the AirCareLabs system, suggested areas for improvement, and interest in using the system; and 4) They will also be asked to identify areas which they feel would most benefit from educational videos or additional documentation/description, and common problems that merit the development of clinical care pathways.

The general structure above will be applied to the following specific user/provider groups:

Patients: We will conduct interviews with three patient groups at various points along the hospital timeline: 1) inpatients, 2) recently discharged patients and 3) patients at 4-6 months follow-up. We have elected to take this approach because the specific challenges a patient faces at each of these time points may differ, and if we wait until the end of the study to interview the patients, they may no longer recall the problems they faced earlier on, for example, during their hospital admission. We will interview at least 10 patients within each of these three groups. Eligible patients will be those admitted with a heart failure exacerbation diagnosis as their primary diagnosis or active heart failure during their hospital course that requires treatment modification. They must also be newly diagnosed with sleep apnea during their admission. The in-patient group will be approached shortly prior to their anticipated discharge date. The recently discharged patients will be interviewed 1-2 weeks post discharge, and the 4-6 month follow-up group will be contacted at 6 months for interviews.

Sleep Technicians: The Sleep Technicians will be responsible for providing overnight assistance to patients that are having difficulty using their PAP at home. The Penn Sleep Center employs over 30 sleep technicians that staff the 28 sleep study beds at 6 different locations. We will randomly invite them to participate and seek to conduct at least ten interviews using the framework described earlier.

Sleep medicine providers (physicians, nurse practitioners, nurses, medical assistants): The sleep medicine staff that provide day-to-day care for patients will be randomly selected for interviews, with at least 15 interviews, of which a minimum of seven will be with sleep medicine physicians.

3.3.1.2 Task 1.2: Develop educational content

Based on the input provided during the one-on-one interviews, we will identify areas of focus that warrant educational videos and brochures. Sample topics include the etiology of sleep apnea, how PAP therapy works, tips for applying masks, and dealing with mouth/nose dryness. [name] will produce at least five educational videos of an average duration of ten to fifteen minutes, and ten brochures that can be viewed from the AirCare system. The Penn Sleep Center has a Sleep Education Unit that will assist with the production of the educational content. This educational unit currently conducts live Webinars, has produced educational videos for display in the patient waiting area, and is active in CME events.

3.3.1.3 Task 1.3: Problem resolution care pathways

The sleep medicine providers and sleep technicians will be contacted by patients through the AirCareLabs system for a variety of problems faced by patients as they start using PAP therapy. Based on the input from the one-on-one interviews, [name] will develop clinical care pathways for resolving the most common problems using evidence-based practices. This will allow for standardized care across different providers. For example, if a patient complains of nasal congestion, one possible set of recommendations would be: 1) three day trial of saline nasal spray; 2) if unsuccessful, five to seven day trial of ipratropium nasal spray; 3) if unsuccessful, review patient nasal spray technique, etc.

3.3.1.4 Task 1.4: Integration of oximeter data

Inclusion of real-time, continuous pulse oximetry data will allow for monitoring a key efficacy measure for PAP: oxyhemoglobin saturation. We will use the iHealth oximeter because of its small size, battery life, low cost, and ability to interface wirelessly via Bluetooth to the AirCareLabs tablet. The unit has an oxyhemoglobin saturation measuring range of 70-99% with an accuracy of $\pm 2\%$ in that range. During Phase I, we will use the available iHealth open API to establish a connection between the AirCareLab system and user data from the oximeter. The system establishes on OAuth client_id and client_secret for each user. The OpenApi can then make requests to the iHealth API Endpoints with the authenticated OAuth credentials. The oximeter itself can store 100 data points, at which time it can send the data, via Bluetooth to the AirCareLab tablet, which will then transmit it via the cellular network to the iHealth server. This data can then be shared with the AirCareLab server using the iHealth OpenApi. The oximeter data can then be queried by users, such as the sleep technician or sleep medicine provider, who wish to monitor the efficacy of the PAP therapy. This powerful technology will allow the sleep medicine team to move beyond simple PAP-derived apnea-hypopnea index values and instead assess the efficacy of treatment on the key endpoint of oxyhemoglobin saturation in a real-time application. We anticipate that the oximeter will be used on a nightly basis for the first week, then as needed if there are continued patient symptoms or any deterioration in the patient's clinical condition.

3.3.1.5 Timeline for Phase 1 Tasks:

| Tasks | Month 1 | Month 2 | Month 3 | Month 4 | Month 5 | Month 6 |
|---|---------|---------|---------|---------|---------|---------|
| Task 1: Structured interviews | | | | | | |
| Task 2: Educational Content | | | | | | |
| Task 3: Problem resolution scripts and Staff training | | | | | | |
| Task 4: Oximetry API connection | | | | | | |

3.3.1.6 Milestones for the Phase 1 project:

1. Structured interviews with users/care providers: Successfully conduct 30 patient interviews, 10 sleep technician interviews, and 15 sleep medicine provider interviews (at least seven with a sleep medicine physician).
2. Educational content: We will create a minimum of five demonstration video clips and ten step-by-step brochures that explain PAP use, mask application, and device care, based on guidance received during the structured interviews.
3. Development of at least ten care pathways to guide sleep technicians and medical assistant staff to assist patients resolve common PAP issues based on focus group work as well as staff training in implementing these scripts.
4. Oximetry data integration using the iHealth API: Successful oximetry data collection will be defined as 1a) maintaining a wireless connection continuously between the AirCare app and the iHealth oximeter for at

least 75% of the study night and 1b) successful transfer of the oximetry data to the central server in 30 minute increments in at least 90% of the cases.

3.3.2. Phase 2 Plan

The goal of Phase 2 is to integrate PAP device data, refine the educational content, develop risk classification content and conduct a randomized controlled trial of the AirCareLab system in a target population of 240 patients.

3.3.2.1 Task 2.1: PAP device data

The PAP devices collect hours of use, estimates apnea-hypopnea index through flow monitoring, and mask leak data on a nightly basis. This data is transmitted wirelessly by modems attached to each unit that connect to the cellular phone network. The large majority of Durable Medical Equipment (DME) providers offer this service since the insurance companies generally require documentation of adherence during the first three months of use to justify continued insurance coverage. This data is stored in a central server maintained by each of the major PAP equipment manufacturers, and is shared with the patient's providers through a web portal data review system. The companies also deliver this data in .csv files on a daily or weekly basis to provider groups, such as the Veterans Affairs administration, large group practices such as the Penn Sleep Center or health systems. The general data format is one row per night of use. During Phase 2, we will integrate this data into the AirCareLabs workflow and make it available to patients and providers directly through the AirCare system. We have elected to perform this in Phase 2 instead of Phase 1 because there are already several commercial platforms that allow for patients and providers to view their PAP-device data, therefore this offers less of a competitive advantage than direct integration of oximetry data, which we have therefore prioritized to Phase 1.

3.3.2.2 Task 2.2: Refine educational content

[figure not shown]
The Educational content created in Phase 1 will be incorporated. Based on the feedback and usage rates of this content, we can then further refine the material. This may include shortening content, adding additional material in a specific section of an existing video/document, or creating new content if necessary. We will be adding a motivational piece, whereby a member of our research staff will contact patients to evaluate their progress and issues while using the PAP unit. Patients will be called on Day 1, 2, 5, 7 and weeks 2, 3, and 4.

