AirCareSystems Group: Study participants in this arm will receive a tablet computer with a pre-installed AirCare application. The tablet will be locked to prevent other usage. All data from previous users will have been wiped from the tablet. The patient will be instructed in the use of the tablet, and will be encouraged to view the installed educational content created in Phase 1.

At the time of discharge, the study participants will leave the hospital with the PAP unit, the tablet computer and an iHealth oximeter. (In the event the patient is discharged before their PSG, they will use the Embletta at-home sleep device to determine eligibility). At home, they will be asked to complete daily, brief questionnaires about their symptoms. They can also use the tablet to submit queries to request assistance with their sleep apnea care. These queries will be answered during the daytime by the day shift sleep technicians or sleep medical assistants according to the standardized care pathways developed earlier. At night, they will be answered by the sleep technicians staffing the 6 active sleep labs (operating seven days a week on all days except national holidays). They will also use the iHealth oximeter on a nightly basis for the first week, then on an as-needed basis thereafter depending upon their symptoms or requests from care providers. It is anticipated that the average study participant will make 2-5 night-time assistance requests, and 3-7 daytime assistance requests. The Risk Classification criteria developed in Task 2.3 will be applied to identify study participants who are at high risk of non-adherence or readmission.

PAP adherence will also be tracked using the built-in device PAP units. Hospital readmissions, ER visits and other doctor visits will also be recorded.

At the end of the first month of treatment, study participants will be asked to return their tablet and iHealth oximeter. They will also be asked to complete the same battery of study survey instruments they completed at the initiation of the study protocol; this will be repeated at six-month follow-up as well.

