Standard Care Group: Study participants in the standard care arm will be asked to complete the same survey instruments shortly prior to discharge. They will leave the hospital with their PAP unit. Out-patient support will be provided by the study participant contacting their Durable Medical Equipment (DME) provider for assistance or their sleep medicine provider through the sleep clinic. At the end of the first month, and again at 6 months, they will be asked to complete the same battery of survey instruments they completed at the initiation of the study protocol. PAP adherence, hospital readmissions, ER visits and other doctor visits will also be tracked

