3.3.2.8 Data Analysis

Descriptive Comparisons Between Intervention Groups at Baseline: Descriptive analyses will be performed in order to characterize the two study groups (AirCare and Standard Care) and to confirm that the randomization resulted in no clinically significant group differences at baseline in demographic, sleep, and other parameters. If the groups differ with regard to baseline variables and these variables are found to have significant associations with outcomes, secondary analysis of covariance will be used to investigate the degree to which estimated relative efficacy depends on these baseline differences.

Hypothesis: The AirCareLabs system will improve PAP adherence post-discharge relative to standard care. Statistical analysis method: PAP adherence will be defined as at least 4 hours of use per night on at least 70% of the study nights (thus, in a typical 30 day month, the study participant will have used it 21 nights for greater than 4 cumulative hours each night); this is consistent with Medicare PAP usage criteria. We will review the PAP adherence downloads, which provide an objective measure of adherence, to determine what percentage of patients in each study arm (AirCare vs. Standard Care) met the adherence criteria (i.e., a patient may be either adherent or non-adherent with PAP). We will utilize a chi-square frequency comparison for this primary analysis.

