3.3.2.9 Sample Size Analysis

The study statistical power will be based on a two-sided Type 1 error rate of 0.05, and a Type 2 error rate of 0.20; these are commonly used criteria for study power calculations.

Hypothesis: We anticipate, based on our preliminary data, that 30% of patients will be fully adherent to PAP therapy (use >4 hours per night for >70% of the month). An improvement in adherence to 50% would represent a clinically meaningful change. Using a power analysis based on the chi-square frequency comparison, we anticipate that a sample size of 93 study participants per group will provide an adequate study power. We will increase this by 30% to factor in study attrition or loss to follow-up, thus a sample size of 120 would be adequate.

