3.3.2.10 Timeline for Phase 2 Tasks

| Tasks | Month 1-2 | Month 3 | Month 4 | Month 5-17 | Month 18-19 | Month 20-23 | Month 24 |
|---|-----------|---------|---------|------------|-------------|-------------|----------|
| Task 1: PAP data integration | ■ | | | | | | |
| Task 2: Refine Educational Content | ■ | | | | | | |
| Task 3: Risk Classification Criteria | | ■ | | | | | |
| Task 4: Study IRB approval | | ■ | ■ | | | | |
| Task 5a: Randomized Clinical Trial: Enrollment period | | | | ■ | | | |
| Task 5b: Randomized Clinical Trial: 6-month follow-up period | | | | ■ | ■ | ■ | |
| Task 6: Data analysis/manuscript generation (30-day readmission analysis) | | | | | ■ | | |
| Task 7: Data analysis/manuscript generation (6-month follow-up analysis) | | | | | | | ■ |

3.3.2.11 Milestones for the Phase 2 project:

1. PAP data integration: Successful oximetry PAP collection will be defined as transfer of the PAP data to the AirCareLabs central server in at least 90% of the study days.
2. Refine educational content: Study participant will be asked to rate their satisfaction with the educational content using visual analogue scales. The educational content will be revised during Task 2.2 in Phase 2. These visual analogue scales will then be repeated during the larger randomized trial (Task 2.4 in Phase 2). Successful completion of this task will be defined as a 20% improvement in study participant satisfaction scores after revising the educational content
3. Risk Classification Criteria: A minimum of ten risk classification criteria will be developed based on review of the data. In our preliminary study, we noted that approximately 70% of study participants were non-adherent to PAP therapy. Thus, successful completion of this milestone will also include the requirement that the ten risk classification criteria flag at least 60-70% of patients as being at risk for non-adherence with PAP therapy.
4. Randomized controlled trial: Successful completion of a randomized controlled trial of 240 study participants, with over 90% study questionnaire data completion.

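### Do the seven scheduled research-staff calls, assigned to no arm in the text, leave the trial's comparison undefined?

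*Combined protocol and SAP*

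**What the plan says.** Section 3.3.2.2, on refining the educational content, closes with a motivational component in which "a member of our research staff will contact patients to evaluate their progress and issues while using the PAP unit". The schedule follows: "Patients will be called on Day 1, 2, 5, 7 and weeks 2, 3, and 4". No arm is named.

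Section 3.3.2.7 randomises participants 1:1 to the AirCare tablet or standard care and then describes each arm. The AirCare paragraph covers the tablet, educational material, oximeter, daily questionnaires, risk flags and help on request: "It is anticipated that the average study participant will make 2-5 night-time assistance requests, and 3-7 daytime assistance requests". The standard care paragraph makes support depend on the participant: "Out-patient support will be provided by the study participant contacting their Durable Medical Equipment (DME) provider for assistance", or else contacting the sleep clinic. Neither paragraph mentions scheduled calls.

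Section 3.3.2.8 reads "Hypothesis: The AirCareLabs system will improve PAP adherence post-discharge relative to standard care". Section 3.3.2.9 starts from "We anticipate, based on our preliminary data, that 30% of patients will be fully adherent to PAP therapy" and plans for a rise to 50%. In 3.3.2.10 the row "Task 2: Refine Educational Content" is placed in Months 1-2, before enrolment in Months 5-17.

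**The concern.** The primary endpoint is PAP adherence, which 3.3.2.8 illustrates over a 30-day month. Seven staff contacts about PAP use, all within about four weeks, bear directly on the behaviour being measured. A reader could reasonably ask whether they belong to the intervention, to both arms, or to preparatory work.

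The answer affects interpretation. If only the AirCare arm is called, a positive result belongs to AirCare plus research-staff calls, while the hypothesis credits the AirCare system. That matters because section 3.4 treats the trial as key to commercialisation. If both arms are called, the comparator is more than the participant-initiated support of 3.3.2.7, and the 30% planning rate may be too low for it.

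**Working it through.** **1. The plan's own figure.** Inputs from 3.3.2.9: control 0.30, AirCare 0.50, two-sided alpha 0.05, power 0.80. With pooled variance and no continuity correction,

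n = [1.960 × √(2 × 0.40 × 0.60) + 0.842 × √(0.30 × 0.70 + 0.50 × 0.50)]² / 0.20²

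= [1.960 × 0.693 + 0.842 × 0.678]² / 0.04 = 93 per group.

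This matches the stated 93. The 30% increase gives 93 × 1.30 = 120.9, against the stated 120 per group and 240 in total. The arithmetic is sound, so the only question is what the two rates describe.

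**2. The call count.** Days 1, 2, 5 and 7 are four calls; weeks 2, 3 and 4 are three. The total is seven.

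**3. Each possible reading.**

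- *AirCare arm only.* This is the likelier reading: the calls sit under AirCare content, and standard care is described as participant-initiated. Randomisation is intact and the chi-square test validly compares the package with standard care. The sample size is unchanged, because 50% is a target for whatever that arm receives. The label is not clearly wrong either: section 3.1.6 already describes AirCare as including staff contact by phone and video, with nurse telephone follow-up.
- *Both arms.* The comparison is unbiased and estimates the effect of AirCare on top of calls. Only the planning rate is in question (step 4).
- *Before the trial.* The calls are not part of the comparison. The timeline allows this, and the second milestone in 3.3.2.11 separates content revision from the randomised trial. A Day 1 to week 4 schedule reads more naturally as a patient's first month on PAP, so this reading is open but not favoured.

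**4. Power if both arms are called.** Power = Φ{[|p₁ − p₂|√n − 1.960√(2p̄(1 − p̄))] / √[p₁(1 − p₁) + p₂(1 − p₂)]}. Every rate pair other than 30% against 50% is an assumption; the documents give no effect for the calls.

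| Control vs AirCare | Power, 93 per arm | Power, 120 per arm | n per arm for 80% |
|---|---|---|---|
| 30% vs 50% (plan) | 80% | 89% | 93 |
| 35% vs 55% | 79% | 88% | 96 |
| 40% vs 60% | 78% | 88% | 97 |
| 35% vs 50% | 54% | 65% | 170 |
| 40% vs 50% | 28% | 34% | 388 |

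An equal lift in both arms costs one or two points of power. The last two rows need three things together: the less likely reading, an assumed lift in controls, and no lift at all from the same calls in the AirCare arm. They show sensitivity to the inputs; they do not show a fault in the plan.

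**The case for a change.** The strongest case for acting is that 3.3.2.7 introduces the arm descriptions as the definition of the treatments, and an intervention aimed at the primary endpoint is missing from both. The callers are research staff, not the sleep technicians and medical assistants who answer queries, so a hospital buying what 3.3.2.7 describes might not receive exactly what was tested. Recruitment extends to further Philadelphia hospitals and to a site in St. Louis, and without a written rule sites could differ in whom they call. One sentence would settle it.

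The factual part stands: the readable text does not assign the calls. A trial report should say who was called. The rest is weaker. A figure in 3.3.2.2 and the flowchart announced in 3.3.2.4 are not available in the text reviewed, and either may make the assignment. Differing site practice is a possibility that nothing in the documents indicates. Even then, participants are randomised individually and the test of equal adherence would hold, with a more mixed description of treatment. The absence of calls from the programme behind the 30% rate is inferred from silence in the short summary in 3.1.3.

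**Conclusion.** The concern is a gap in description and does not call for a change to the plan. The contrast is stated, the sample size reproduces at 93 per group, and the primary analysis is valid under all three readings. On the likeliest one, calls in the AirCare arm only, neither power nor the test changes, and the result is read as that of AirCare including its scheduled staff contact. If both arms are called and benefit equally, power at 93 per group is 78-79% against a planned 80%.

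This rests on two assumptions: that the calls follow one rule across sites, and that any benefit of calling controls would be shared to a similar degree by AirCare participants. The documents contradict neither. The study team will know who was called, and analysts can describe the arms accordingly. No stated rule or number is shown to give a wrong result.
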